### **6.3. Early Withdrawal**

If subject withdraws from the study after the screening visit, no further evaluations are necessary. If subject withdraws from the study after visit 2, all safety assessments will be performed (see section 6.2.4.) and the investigators will be unblinded. For specific laboratory assessments refer to Table 1 Laboratory Assessments (see section 6.10.).

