#### **6.2.4. Visit 4: (Safety Visit)**

- Collect laboratory samples for screening assessment, for specific tests refer to Table 1.

- Complete physical exam, including neurological exam. Collect vital signs, height and weight prior to ECG and blood draw.
- Perform a standard 12-lead ECG.
- Record AEs/SAEs.

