### **7.3. Treatment Assignment**

Randomization will be stratified by gender *a priori* by the permuted block method. Sequences will be assigned for each gender by random selection of one of the twenty permutations of block of size 6 such that 3 of each gender are allocated to group 1, and 3 of each gender are allocated to group 2. The trial is a double blinded study so that neither the subject, the investigator, nor the trial coordinator will know to which sequence the subject has been randomized. To facilitate subject blinding, all subjects will undergo the same follow-up procedures. One clinician at the site will be unblinded to randomization and prepare the study dose for each subject. This person will not have responsibility for obtaining any study data. The investigators will be provided

with a sealed envelope containing the true sequence of glulisine and saline for each group if the blind needs to be broken due to unforeseen circumstances.

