#### **8.2. Subject Withdrawal**

Subject may withdraw from study at any time for any reason without penalty or be terminated from the study by the clinical investigator (see provisions for termination by study team.) Investigational team will document the reason(s) for withdrawal. In the event a subject chooses to withdraw from study before Visit 4 the safety procedures described in Section 6.2.4. and will be performed ideally within 14 days following subject's decision to withdraw. For all subjects who withdraw, all final safety assessments will be collected regardless of time elapsed since previous visit. In addition to final visit, subjects who withdraw early will be contacted within 7 days by study staff via telephone to assess development of new and/or ongoing AEs and concomitant medications. Efforts will be made to recruit subjects to replace any withdrawals so as to maintain an n=12.

Subject's participation may be terminated at the discretion of the investigator. Individuals may be withdrawn for the following reasons:

- Clinically significant adverse events
- Lost to follow-up
- Protocol violations
- Inability to tolerate study medication
- Other

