### **11.5. Provision of Study Results and Information to Investigators**

Study results will be made available by the study statistician once analysis (Interim Analysis) is complete. Study Staff will not be unblinded in regards to individual subjects randomization status until after the database is locked.

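### Section 6.3 unblinds the investigators at any withdrawal after Visit 2, which conflicts with 11.5 and does not fix whether the subject's last adverse event judgements come first

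*Combined protocol and SAP*

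**What the plan says.** Four sections of the combined protocol and SAP bear on this.

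- **6.3 (Early Withdrawal):** the rule reads "If subject withdraws from the study after visit 2, all safety assessments will be performed (see section 6.2.4.) and the investigators will be unblinded". No reason, medical need or time is attached to the unblinding.
- **11.5 (Provision of Study Results):** "Study Staff will not be unblinded in regards to individual subjects randomization status until after the database is locked". No exception is named.
- **7.3 (Treatment Assignment):** "neither the subject, the investigator, nor the trial coordinator will know to which sequence the subject has been randomized". A sealed envelope is held for use "if the blind needs to be broken due to unforeseen circumstances".
- **8.2 (Subject Withdrawal):** for a subject who leaves before Visit 4, the safety procedures of 6.2.4 "will be performed ideally within 14 days following" the decision to withdraw. In addition, "subjects who withdraw early will be contacted within 7 days by study staff via telephone to assess development of new and/or ongoing AEs". The start of the 7 days is not given, and neither contact is tied to the unblinding.

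The 6.2.4 procedures include "Record AEs/SAEs" as well as examination, laboratory samples and ECG.

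**The concern.** The protocol gives site staff two instructions that differ. On a withdrawal before lock, 6.3 tells them to unblind the investigators and 11.5 tells them not to.

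The primary endpoint (3.3) is the incidence of adverse events, counted both overall and as treatment-related. Under 9.1 and 9.2.1, whether an abnormal finding counts as an adverse event depends in part on whether the investigator thinks it clinically significant. If the investigator already knows the treatment when making the last such judgements for a withdrawn subject, those judgements lose the protection of the blind. Adverse events already recorded at the dosing visits come before the trigger and are not exposed.

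**Working it through.** **1. Do the rules conflict?** Take a subject who withdraws after Visit 2 and before lock.

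| Section | Is the investigator unblinded? | Condition stated |
|---|---|---|
| 6.3 | Yes | None beyond withdrawal after Visit 2 |
| 7.3 | No, unless the code is broken | Unforeseen circumstances |
| 11.5 | No, until lock | No exception |

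Withdrawal is planned for in 8.2, so it fits poorly under the unforeseen circumstances of 7.3. Taking the investigators out of the term study staff in 11.5 has no support: that section's heading is about information to investigators, and 7.3 lists the investigator among those blinded.

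**2. Is the order fixed?** Section 6.3 names the 6.2.4 assessments first and the unblinding second, which suggests that sequence. The two are joined only by a conjunction, and performing an assessment is not the same as finalising the judgement on it. The 8.2 call is not mentioned in 6.3. The visit target is 14 days from the decision to withdraw. If the 7 days for the call run from that visit, the last contact falls at 14 + 7 = 21 days. Both are targets and not upper limits, since 8.2 asks for the final assessments however much time has passed.

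**3. Who is covered?** Section 6.3 speaks of a subject who withdraws, while 6.5 distinguishes subjects who withdraw from those who are withdrawn. The list of reasons in 8.2, which includes "Clinically significant adverse events", follows the sentence on termination by the investigator. Whether 6.3 reaches those subjects is not stated.

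**4. How large could the effect be?** Inputs from 10.4: n = 12, alpha 0.05, differences of 1.5 and 2.0 adverse events, SDs of 1.0, 1.5 and 2.0.

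- *The plan's own figures.* Paired t-test, two-sided, 11 degrees of freedom, noncentrality = (difference/SD) × √12. This gives 0.997, 0.883 and 0.658 for a difference of 1.5, and 1.000, 0.987 and 0.883 for 2.0. All six match the table, so its SD is that of the paired differences.
- *Subjects exposed per withdrawal.* 1 of 12 (8%), or mainly one period of 12 × 2 = 24 (4%). Section 8.2 replaces withdrawals, so these denominators are approximate. One withdrawal before Visit 3 plus a replacement who completes gives 13 subjects and 25 periods.
- *One misjudged event in a subject with both periods.* Shift in the mean paired difference = 1/12 = 0.083. Relative to 1.5 this is 5.6%; relative to 2.0 it is 4.2%.
- *In standard errors.* SE = SD/√12 = 0.289, 0.433 and 0.577 at SDs of 1.0, 1.5 and 2.0. The shift of 0.083 is then 0.29, 0.19 and 0.14 SE.

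The shift does not apply to a subject who leaves between Visits 2 and 3, who has no pair. It uses the simplification of 10.4 and not the mixed-effects Poisson model of 10.2.

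**The case against.** The strongest reply is that 6.3 may be a deliberate, specific exception to the general rules in 7.3 and 11.5. The subject receives no further study treatment, and the sentence already puts the recording of adverse events before the unblinding. On this view only a cross-reference is missing. That reading is possible, and unblinding at withdrawal is a choice open to the sponsor. But nothing in 11.5 or 7.3 says that such an exception exists, and 6.3 does not settle when the unblinding happens relative to the final records.

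Several limits on the concern stand:

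- The 8.2 call is made by study staff, while 6.3 unblinds only the investigators.
- The documents do not say who judges relatedness. Exposure of that judgement is an inference; exposure of the clinical-significance judgement follows from 9.1 and 9.2.1.
- Section 9.2.2 describes recording of adverse events as running until withdrawal or completion, so it is not certain that events first reported at the later call enter the endpoint.

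A reader might also infer that 6.3 unblinds everyone who stops because of an adverse event. The documents do not support that: the reasons list in 8.2 concerns termination by the investigator, whose inclusion in 6.3 is unclear. A subject may still leave voluntarily because of an adverse event, so the concern is narrowed but not removed.

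**Conclusion.** The conflict between 6.3 and 11.5 is real and no other section resolves it. The consequence is a limited one: late adverse event and clinical-significance judgements in a withdrawn subject could be made with treatment known.

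The size is small and only illustrative: about one subject per withdrawal, out of roughly 12 plus replacements, and 0.14 to 0.29 SE for each misjudged event in a subject with both periods. This assumes that the paired simplification of 10.4 is an adequate guide; it is not an effect computed under the planned Poisson model. The documents give no withdrawal rate after randomization, so no probability that the rule is triggered can be stated.

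A reader might go further and infer that one withdrawal would unblind the whole trial, because the 7.3 envelope holds the sequence for each group. That would require the site to know which group each subject belongs to, which is not stated. Nor do the documents show that the primary result would be materially biased. This is a wording defect that should be corrected because it affects blinding on an endpoint that rests partly on judgement.

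**What to change.** Reconcile 6.3, 7.3, 8.2 and 11.5 in one of two ways.

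1. State that withdrawal alone does not break the blind before database lock. Keep the 7.3 code break and name it in 11.5 as the exception.
2. If the sponsor keeps unblinding at withdrawal, state in 6.3 that it happens only after the 6.2.4 assessments and the 8.2 call are done and all of that subject's adverse event, clinical-significance and relatedness records are final. State whether the rule covers subjects terminated by the investigator, and cross-reference it in 11.5.

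Either takes a few sentences. The cost is that investigators learn a withdrawn subject's treatment later, or not by default. Code-breaking under 7.3 is unaffected, and the sample size and the power table do not change.

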### **6.4. Safety**

For all safety assessment described below, any clinically significant change will be recorded as an AE or SAE.

### **6.5. Physical Examination**

Complete physical examination will be performed at visits 1 and 4 or if the subject withdraws or is withdrawn from the study early. Any abnormalities noted at Visit 1, will be documented as part of the subject's medical history.

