### **6.6. Neurological Examination**

Neurological examination will be performed at visits 1 and 4 or if the subject withdraws early. Any abnormalities noted at Visit 1, will be documented as part of the subject's medical history.

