### **6.9. ECG**

A standard 12-lead ECG will be performed on all subjects at baseline and visit 4.

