#### **9.2.1. Clinical Laboratory Abnormalities and Other Abnormal Assessments as AEs and SAEs**

Any new abnormal, vital, examination, or laboratory finding judged clinically significant by the investigator will be documented as an AE or SAE, if meeting the definitions for such. Abnormal lab findings or other abnormal assessments associated with the disease under study will not be considered AEs or SAEs unless more severe than expected, as judged by the investigator.

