## **10. DATA ANALYSIS AND STATISTICAL CONSIDERATIONS**

### **10.1. Statistical Analysis**

All primary and secondary endpoints will be summarized within strata defined by treatment and study period.

Treatment effects on both primary and secondary endpoints will be assessed using common statistical methodology for crossover trials. Continuous outcomes, such as the FOME and the RBMT-C, and count outcomes, such as adverse event incidence, will be analyzed using a mixed-effects linear model to account for period effects and patient characteristics such as age and sex. Plots of the observed effects will be constructed to aid with interpretation.

All statistical analyses will be completed using SAS® software. Visual representations of the data will be constructed using the package ‘ggplot2’ in R [63, 64].

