## **10.2. Safety Outcomes**

The primary endpoint is defined as the ‘incidence of any or related adverse and/or serious events of intranasal glulisine versus placebo.’ The difference in incidence of adverse events between subjects receiving glulisine and those receiving saline will be modeled in terms of rates using a mixed-effects Poisson regression model accounting for period and the treatment-period interaction as well as subject age and sex.

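### Do examination and ECG findings first seen at Visit 4 spoil the glulisine-versus-placebo adverse event comparison?

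*Combined protocol and SAP*

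**What the plan says.** Three safety checks are done only before and after the whole treatment phase:

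- Section 6.5: "Complete physical examination will be performed at visits 1 and 4 or if the subject withdraws or is withdrawn from the study early".
- Section 6.6: "Neurological examination will be performed at visits 1 and 4 or if the subject withdraws early".
- Section 6.9: "A standard 12-lead ECG will be performed on all subjects at baseline and visit 4".

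The Visit 4 list in section 6.2.4 agrees: "Complete physical exam, including neurological exam. Collect vital signs, height and weight prior to ECG and blood draw". The lists for Visits 2 and 3 (sections 6.2.2 and 6.2.3), where the randomized doses are given, include none of the three.

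Positive findings count as adverse events. Section 6.4 says "any clinically significant change will be recorded as an AE or SAE", and section 9.2.1 says a new "finding judged clinically significant by the investigator will be documented as an AE or SAE" if it meets the definitions.

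The analysis needs a period and a treatment for each event. Section 10.1: "All primary and secondary endpoints will be summarized within strata defined by treatment and study period". Section 10.2 has the difference in incidence "modeled in terms of rates using a mixed-effects Poisson regression model accounting for period and the treatment-period interaction", with age and sex as further terms. Section 10 does not say how an event of unknown onset is assigned, and it gives no separate analysis of the physical examination measure named in section 3.5.

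**The concern.** A change with no symptoms that is first noticed at Visit 4 could have arisen after either dose. The model needs a label that nobody observed, and a period term cannot supply it. If glulisine caused the change and it lasted, it would turn up about equally in both sequences, and the between-treatment comparison would miss it.

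The comparison would then lean toward no difference, which is the favourable answer in a safety trial. Safety is a primary objective and the adverse event comparison is the primary endpoint, so a reader might take a null result on these checks as evidence that glulisine behaves like placebo. Choosing the label after unblinding would also leave some discretion in the analysis of 12 subjects.

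**Working it through.** **Inputs.** From section 10.4: n = 12, alpha 0.05, paired means, differences of 1.5 and 2.0 events, SD 1.0 to 2.0. From section 7.3: three of each gender per sequence, so six per sequence. Not in the documents and therefore assumed: p, the chance that one glulisine dose causes a silent, clinically significant change on one of these checks. The range shown is 0.02 to 0.25.

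**1. The plan's own power table.** Two-sided paired t-test, 11 degrees of freedom, noncentrality difference/(SD/√12). This gives 0.997, 0.883, 0.658, 1.000, 0.987 and 0.883, matching all six entries.

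**2. What labelling does to a persistent finding.** Suppose every such change lasts to Visit 4. The glulisine-first sequence then has 6p findings and the placebo-first sequence has 6p.

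- Last-dose label: 6p go to placebo and 6p to glulisine; contrast 6p − 6p = 0.
- First-dose label: 6p to glulisine and 6p to placebo; contrast 0.
- Both doses: 12p to each; contrast 0.

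The concern is right that the expected contrast vanishes. For the same reason, none of these labelling rules brings it back.

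**3. Effect on power.** If p of the 1.5-event difference is of this kind, the recorded difference is 1.5 − p. With SD held at 1.5:

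| p | Recorded difference | Share lost (p/1.5) | Power |
|---|---|---|---|
| 0 | 1.50 | 0 | 0.883 |
| 0.02 | 1.48 | 1.3% | 0.875 |
| 0.05 | 1.45 | 3.3% | 0.861 |
| 0.10 | 1.40 | 6.7% | 0.837 |
| 0.25 | 1.25 | 16.7% | 0.748 |

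The last row needs one single dose in four to cause a silent, clinically significant, lasting change. Nothing in the documents supports that rate.

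**4. Does leaving the findings out help?** Assume 12 datable events on glulisine and 6 on placebo. With Visit 4 findings included under the last-dose label, the difference is (12 + 6p) − (6 + 6p) = 6. With them left out it is 12 − 6 = 6. The two are identical for every p, so a sensitivity analysis of that kind cannot show the problem on the scale used for planning.

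**5. Do background findings distort the ratio?** Let b be the rate per subject of Visit 4 findings not caused by the drug. With the last-dose label the ratio is (12 + 6b)/(6 + 6b), for example 1.91 at b = 0.10. But if those 12b findings arose evenly over the two periods and were dated perfectly, they would also split 6b and 6b and give the same ratio. This is what any non-drug event does to an all-event ratio; the schedule does not cause it.

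**6. Crude ratios are not the planned model.** At p = 0.25 with full persistence, the crude ratio is (12 + 1.5)/(6 + 1.5) = 1.80. Section 10.2 includes a treatment-period interaction. Splitting the datable events evenly by period, period 1 gives 6/3 = 2.00 and period 2 gives 7.5/4.5 = 1.67; the log-scale average is √(2.00 × 1.67) = 1.83. Crude ratios therefore do not measure the effect on the planned analysis.

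**7. What stays visible.** The Visit 1 to Visit 4 change is seen in every completer. With full persistence, the chance of at least one drug-caused finding among 12 is 1 − (1 − p)^12: 22%, 46%, 72% and 97% for p = 0.02, 0.05, 0.10 and 0.25.

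**The case for a change.** The best case for a change is that it costs only wording. Since section 10.1 asks for summaries by period, somebody must assign these events, and it is cleaner to fix the rule before unblinding. With small counts, one or two unplaceable findings could matter. A separate table by sequence would also report the section 3.5 physical examination measure, and a sentence could warn against reading a null on these checks as evidence of safety.

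Part of this stands. The schedule is read correctly and the plan is silent on events of unknown onset. But assigning such an event to the last treatment received is the usual dating convention, and step 2 shows that it yields no contrast for a persistent effect. The sensitivity analysis changes nothing on the difference scale. What is left is a listing and a caveat, which an analyst can add at the reporting stage without amending the plan. No passage says that a null on these checks will be read as equivalence.

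The affected events are also few in kind. They must be free of symptoms and missed by the vital signs and oxygen saturation taken around each dose, by the adverse event recording at Visit 3 and by the 24-hour calls. They must occur in a completer and still be present at Visit 4. The test placebo dose before randomization, which section 6.2 does not assign to a visit, is a separate documentation gap and alters none of the figures.

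**Conclusion.** The observation is true, but it does not call for a change. In completers, the physical examination, neurological examination and ECG cannot support a glulisine-versus-placebo contrast for silent findings that persist to Visit 4. That follows from the visit schedule, and analysis wording cannot repair it; the one step that would is a further check between the doses, which is an added procedure.

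The size depends wholly on p, which the documents do not give. If p is 0.10 or less, power in the 1.5/1.5 scenario stays at 0.837 or above, against the stated 0.883. The calculation assumes six completers per sequence, full persistence and an unchanged SD. The only experience with this drug reported in the introduction (nine subjects with Alzheimer's disease, a different device) was described as safe and well tolerated, so p may be close to zero.

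For a single-dose pilot of 12 subjects, checking these three measures before and after the treatment phase is a fair trade-off. Listing Visit 4 findings by sequence, as change from Visit 1, is sensible reporting that the plan already permits.

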### **6.6. Neurological Examination**

Neurological examination will be performed at visits 1 and 4 or if the subject withdraws early. Any abnormalities noted at Visit 1, will be documented as part of the subject's medical history.

### **6.7. Vital Signs**

Vital signs and O2 saturation will be recorded at visits 1, 2, 3, and 4. For within subject consistency, brachial artery pressure will be obtained in the routine fashion, the same arm will be used for all study measurements.

Blood pressure and heart rate to be measured after subject has been sitting quietly for a minimum of 5 minutes. Diastolic blood pressure will be measured at the disappearance of Korotkoff sounds. Vitals sign and O2 saturation will be monitored by clinical staff during each visit of the study.

In addition, vital signs and O2 saturation will be measured pre and post study dose on Visits 2 and 3. The investigator will be notified for any baseline changes in blood pressure >20 mmHg systolic and >10mmHg diastolic or O2 saturation < 90%.

A baseline pre-dose fingerstick blood glucose will be measured followed by measurements post-study drug at 30 minutes. The investigator will be notified for any baseline changes. Percentage change from baseline glucose will be calculated as follows: [(pre-insulin serum glucose – post-insulin serum glucose) / (pre-insulin serum glucose)] x 100%. Any change >10% will be considered clinically significant.

Vital signs will be taken prior to ECG and blood draw.

